8.1.2 Main study

Sample size calculations below are for the full phase II studies based on progression-free survival (PFS):

CHRONOS-A: Progression-free survival (PFS) in our population at 5-years is approximately 85-90% after radiotherapy and similar for prostatectomy. Overall survival is high and being a 10-15 year outcome it will not be used in this study. PFS is a clinically meaningful endpoint, with precedence in other studies and can be measured in the same way in both arms (time to salvage therapies). Our hypothesis is that FT is non-inferior in terms of PFS, whilst having fewer side-effects. The question is what margin of non-inferiority should be in the main study. In the CHHIP radiotherapy RCT a 20% relative change was acceptable as a non-inferiority margin comparing one form of radiotherapy to another form of radiotherapy HR 1.208; absolute difference 5%). In the PART RCT pilot (prostatectomy versus FT), a failure of 25% (PFS 75%) for surgery compared to a maximum 35% after focal (PFS 65%) was accepted by the NIHR-HTA as a non-inferior design because the functional detriment would be substantially better.

For a patients' perspective, we can look at the unpublished NCRN COMPARE study (presented at NCRI UK Annual Conference, November 2018). This was a discrete choice experiment where 544 newly diagnosed men (~30 UK centres) were asked to make choices between different treatment scenarios. Marginal Rate of Substitution (MRS) were calculated (trade-offs men are willing to make between side-effects and survival). On average men are willing to trade 0.68% of survival chance against 1% chance of improving urinary function, with PFS and sexual function MRS at 0.41% and 0.28%. Based on the above, it is reasonable to assume 85% PFS after radiotherapy with a non-inferiority margin of 5% for FT would meet clinical and patient acceptance.

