Based on an allocation ratio of 1:1 and a non-inferiority margin of 0.05 with a 0.85 PFS rate in the standard care arm (at median 5-years), power 0.80 and alpha 0.05, drop-out after randomisation of 5%, the overall required sample size is 1190 with 136 expected total number of events. Total recruitment and follow-up period will be 8 years. If recruitment rates were deemed to be high then the power could be adjusted to 0.90 and the total sample size will be 1660 with 189 expected total number of events. This will be on the advisement of the TSC. PFS for the main Stage will be defined as transition to salvage therapies or metastases or mortality related to prostate cancer.

CHRONOS-B main stages II and III: Using the latest update of –nstage-, with an allocation ratio of 1:1:1, we anticipate approximately 1200 patients are required over 5 years to observe 120 control arm failure-free survival (FFS) events within 7.6 years. This time will be dependent on observed FFS event rates and is based on an assumption of 20 patients recruited per month. This calculation gives 85% power at the efficacy stage analysis, to detect a hazard ratio (HR) of 0.67 and is based on 20% of patients having a FFS event by 3 years (30% by 5-years).

Table 1. Sample size calculations

	Short Title: IP4 - CHRONOS	Protocol No: 19CX5006	Sponsor: Imperial College London	Version: 5.0 Date: 13 th July 2022
١				10 Gary Lore

	Stage 1	Stage 2	Overall
Alpha	0.45	0.025	0.044
Power	95%	85%	83%
Critical HR (guidance for stopping early)	0.974		-
Control Arm Events	47	120	-
Accrual	20pts/m	20pts/m	20pts/m
Cumulative Patients	1003	1200	-
Time to analysis (years)	3.4	4.2	7.6

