8.3 Statistical analysis

Feasibility and pilot study

The primary analysis of the feasibility stage will estimate recruitment and randomisation rate to allocated arm. Safety in terms of Adverse Events will be analysed in terms of occurrence of adverse events in each arm.

The main study will be initiated if the minimum target recruitment rate of the feasibility study is within the lower end of the confidence interval and funding has been confirmed.

Main study

Time-to-event (progression or failure depending on which of CHRONOS-A or CHRONOS-B) data will be presented using Kaplan-Meier plots. In all time-to-event analyses, patients that have not experienced the event in question will be censored at the date last seen/known to be alive. The hazard ratio (HR) will be taken from a Cox proportional hazards model, adjusted for any stratification factors used at randomisation. Differences in time-to-event outcomes will be assessed using the log-rank c2 test and expressed using a hazard ratio (HR) with a 2-sided 95% confidence interval. If there is evidence of non-PH in the treatment

Protocol No: 19CX5006 v5.0 13th July 2022

Short Title: IP4 - CHRONOS	Protocol No: 19CX5006	Sponsor: Imperial College London	Version: 5.0 Date: 13 th July 2022
			13 July 2022

effect, the HRs are difficult to interpret and the restricted mean survival time (RMST) constructed from a flexible parametric model with time varying treatment effects will take primacy.

The assumption of proportional-hazards (PH) will be tested and appropriate methods applied to the data in the case of any violation. If there is no evidence of non-PH in the treatment effect, the HR for the adjusted Cox model takes primacy. If there is evidence of non-proportional hazards in the treatment effect, the HRs are difficult to interpret and the restricted mean survival time constructed from a flexible parametric model with time varying treatment effects will take primacy.

Planned interim and sub-group analyses: Each research comparison will have a pilot stage, one pre-planned interim analysis on PFS or FFS if the research comparison were to continue to a main stage study, and a final efficacy stage on PFS or FFS.

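### CHRONOS-A's own figures show it was sized at one-sided 5%, the only interval planned is two-sided 95%, and no non-inferiority decision rule connects the two

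*Protocol*

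**What the plan says.** Protocol section 8.1.2 sets "a non-inferiority margin of 0.05 with a 0.85 PFS rate in the standard care arm" and gives "power 0.80 and alpha 0.05, drop-out after randomisation of 5%, the overall required sample size is 1190 with 136 expected total number of events". If recruitment is fast, "the power could be adjusted to 0.90 and the total sample size will be 1660 with 189 expected total number of events". No sidedness is attached to the alpha.

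Protocol section 8.3 covers the time-to-event outcomes of both trials in one paragraph. Differences are examined with the "log-rank c2 test and expressed using a hazard ratio (HR) with a 2-sided 95% confidence interval". No other interval is specified. The adjusted Cox hazard ratio has primacy under proportional hazards; otherwise restricted mean survival time (RMST) does.

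For CHRONOS-B, Table 2 in section 8.3 labels its alpha as one-sided and sets 0.025 for the efficacy stage. CHRONOS-A has no such label. Neither section says which confidence limit is compared with which margin, and the CHRONOS-A margin is never given as a hazard ratio. The SAP covers only the feasibility stage and does not address this.

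**The concern.** In a non-inferiority trial the alpha and the deciding interval are one choice. Requiring the upper limit of a two-sided 95% interval to lie below the margin is a one-sided 2.5% test; using a two-sided 90% interval is a one-sided 5% test. If the trial is sized at 5% and read from the 95% interval, it has less power than stated. If it is read at 5%, the risk of a false non-inferiority claim is twice what a reader would assume from the 95% interval. With no rule written down, the level could be settled after the data are seen, and this is the main claim of CHRONOS-A.

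**Working it through.** **Inputs (Protocol 8.1.2 and 8.3).** Alpha 0.05; power 0.80 with 136 events and 1190 patients; power 0.90 with 189 events and 1660 patients; control PFS 0.85; margin 0.05; 1:1 allocation; 5% drop-out; two-sided 95% interval. Normal quantiles: 1.645 (one-sided 5%), 1.960 (one-sided 2.5%), 0.842 (80% power), 1.282 (90% power).

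**Step 1. Which alpha was used?** Under standard formulas, required events are proportional to (z_alpha + z_power)². The ratio of the 80% design to the 90% design therefore depends on alpha, not on the margin or event rate.

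| Source | Ratio |
|---|---|
| Plan, events: 136/189 | 0.720 |
| Plan, patients: 1190/1660 | 0.717 |
| One-sided 5%: (1.645+0.842)²/(1.645+1.282)² | 0.722 |
| One-sided 2.5%: (1.960+0.842)²/(1.960+1.282)² | 0.747 |

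Solving for alpha gives 0.053 from the events (0.047 to 0.058 allowing for rounding) and 0.056 from the patient numbers. Both point to one-sided 5%.

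**Step 2. Reproduce the event counts.** Freedman's formula is events = [(HR+1)/(HR−1)]² × (z_alpha + z_power)². With HR = ln(0.85)/ln(0.90) = 1.5425, the first factor is about 21.96.

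| Level | 80% power | 90% power |
|---|---|---|
| One-sided 5% | 136 | 189 |
| One-sided 2.5% | 173 | 231 |

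The first row matches the plan exactly. Schoenfeld's formula at one-sided 5% gives 132 and 183, which is close but not exact.

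**Step 3. Power if the 95% interval decides.** Taking the stated power as correct at one-sided 5%, power at one-sided 2.5% is Φ(z_power + 1.645 − 1.960):

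- 80% design: Φ(0.527) = 0.70.
- 90% design: Φ(0.967) = 0.83.

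Restoring 80% needs (1.960+0.842)²/(1.645+0.842)² = 1.27 times the events. That is 173 events, or about 173 × 1190/136 = 1514 patients at the plan's own patients-per-event ratio.

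**Step 4. What it means for a result.** With 136 events the standard error of log HR is about 2/√136 = 0.1715. Against a margin of 1.5425 (log 0.4334), the largest observed HR that would pass is:

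- 90% interval: exp(0.4334 − 1.645 × 0.1715) = 1.16.
- 95% interval: exp(0.4334 − 1.960 × 0.1715) = 1.10.

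**Step 5. Is the reproducing pair the stated pair?** No. Step 2 needs 0.90 versus 0.85. The stated control PFS of 0.85 with a 0.05 margin gives 0.85 versus 0.80, HR = ln(0.80)/ln(0.85) = 1.373. Power is Φ(√events × (HR−1)/(HR+1) − z_alpha):

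| Events | One-sided 5% | One-sided 2.5% |
|---|---|---|
| 136 | 57% | 45% |
| 189 | 70% | 58% |

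On that pair, 80% power needs 251 events at one-sided 5% or 318 at one-sided 2.5%.

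**The case against.** A reader might infer that sections 8.1.2 and 8.3 contain two conflicting pass rules, so that a borderline result passes under one and fails under the other. The documents do not support that. Neither section prints a non-inferiority rule. Section 8.3 says how differences are tested and expressed for both trials together, not that the 95% interval decides CHRONOS-A. A one-sided 5% decision with a 95% interval reported alongside is compatible with the text. The log-rank test adds nothing, because it is a test of difference. What the documents show is a missing rule, and this part of the objection stands.

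Sidedness is also inferred rather than printed. A proportions formula with 0.90 in both arms, margin 0.05, one-sided 0.025 and 5% drop-out gives 1192, so the headline sample size alone does not settle it. That reading fails elsewhere: at 90% power it gives 1594 rather than 1660, and its 1132 evaluable patients at a 10% event rate would yield about 113 events, not 136. The inference to one-sided 5% holds.

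A second tempting reading is that 70% and 83% are the power on the plan's own inputs. They are not, as step 5 shows. Nor is the loss the same whatever the margin, unless the stated 80% and 90% are first taken as correct.

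Finally, the main stage depends on funding, and SAP section 6.6.2 allows its sample size to be revisited for compliance and feasibility results. No CHRONOS-A efficacy analysis is imminent. That leaves time to settle the rule but does not supply it.

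**Conclusion.** CHRONOS-A was sized at one-sided 5%. The only interval the plan offers corresponds to one-sided 2.5% if non-inferiority is read from its upper limit, and nothing says whether it is to be read that way. If it is, the stated power is not delivered: about 70% instead of 80%, and 83% instead of 90%. These figures assume that the stated power is right at one-sided 5%, which the event counts support only for 0.90 versus 0.85 (HR 1.54). On the stated 0.85 control and 0.05 margin, power is already about 57% and 70% at one-sided 5%, falling to 45% and 58% at one-sided 2.5%. That mismatch is separate, and changing the interval level will not cure it. An observed hazard ratio between about 1.10 and 1.16 (136 events, margin 1.54) is where the undecided level would change the conclusion.

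**What to change.** State three things together in Protocol sections 8.1.2 and 8.3: the sidedness of alpha, the level of the deciding interval, and the margin on that interval's scale, meaning the hazard-ratio equivalent of the 5-point PFS margin. Because section 8.3 lets RMST take primacy under non-proportional hazards, give a margin on that scale too. Then choose one of:

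- **(a)** One-sided 0.025, with the upper limit of the two-sided 95% interval deciding and CHRONOS-A power restated at that level. This matches the efficacy-stage alpha of CHRONOS-B.
- **(b)** One-sided 0.05 written out in 8.1.2, with the two-sided 90% interval deciding in 8.3 and the 95% interval descriptive. The stated event counts are unchanged.

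Under either option, recompute the printed power from the control PFS and margin finally adopted; do not carry over 70% and 83%.

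The cost of the wording is small. Option (a) means a less favourable stated power or, to keep the target on the HR 1.54 basis, 173 events (about 1514 patients) for 80% or 231 events (about 231 × 1660/189 = 2029 patients) for 90%. Option (b) makes a more lenient error rate explicit, which the sponsor would have to defend.

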11.10 Publication and Dissemination policy	60
12. REFERENCES	62
SIGNATURE PAGE 1 (Chief Investigator)	64
SIGNATURE PAGE 2 (Sponsor)	65

Short Title:	Protocol No:	Sponsor:	Version: 5.0
IP4 - CHRONOS	19CX5006	Imperial College London	Date:
			13 th July 2022

SIGNATURE PAGE 3 (Statistician)66	
SIGNATURE PAGE 4 (Principal Investigator)67	

TRIAL SUMMARY

TITLE	Comparative Health Research Outcomes of NOvel Surgery in prostate cancer			
AIM	To deliver an overarching RCT framework to efficiently evaluate novel surgical techniques in the treatment of non-metastatic prostate cancer			
	CHRONOS-A Pilot: To determine if men will agree to participate in an RCT that randomly assigns them to focal therapy alone or radical therapy (radiotherapy or prostatectomy).			
	Main: To determine if focal therapy alone is non-inferior when compared to radical therapy (radiotherapy or surgery) in terms of progression-free survival (PFS) at 5 years in men with clinically significant non-metastatic cancer.			
	CHRONOS-B Pilot: To determine if men expressing a preference for focal therapy will agree to participate in a multi-arm, multi-stage (MAMS) RCT that randomly assigns them to focal therapy alone or focal therapy in combination with neoadjuvant and/or adjuvant agents.			
	Main: To determine if focal therapy combined with neoadjuvant and/or adjuvant agents, compared to focal therapy alone, will improve failure-free survival (FFS) at 5 years, in men with clinically significant non-metastatic cancer			
PHASE	Phase II Randomised Control Trial (RCT) incorporating an internal pilot			
DURATION	Pilot: Recruitment 12 months. Minimum 3 months follow-up. Total 15 months. Main study: Recruitment further 48 months. Total including follow-up = 96 months			
DESIGN	Randomised controlled trial Two linked RCTs with CHRONOS-A and CHRONOS-B discussed with patients and choice of A or B dependent on physician and patient equipoise.			
	- CHRONOS-A Two arm RCT			
	- CHRONOS-B Multi-Arm Multi-Stage (MAMS) Randomised Control Trial			

Short Title: IP4 - CHRONOS	Protocol No: 19CX5006	Sponsor: Imperial College London	Version: 5.0 Date: 13 th July 2022
			10 daily 2022

SAMPLE SIZE	Eggeihility/nilot		
SAIVIPLE SIZE	Feasibility/pilot		
	CHRONOS-A 60 patients over 12-months (These participants will form part of the main study if feasibility is met and funding obtained)		
	CHRONOS-B 60 patients over 12-months (These participants will form part of the main study if feasibility is met and funding obtained)		

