2.7 Summary Table of Objectives and Endpoints

Protocol No: 19CX5006 v5.0 13th July 2022

Short Title:	Protocol No:	Sponsor:	Version: 5.0
IP4 - CHRONOS	19CX5006	Imperial College London	Date:
			13 th July 2022

Study stage	Objectives	Endpoints	Time-point(s) of evaluation of this endpoint (if applicable)
Pilot	Primary	As above	At time of consent (acceptance to randomisation) and at time to treatment (compliance)
Pilot	Secondary	As above	At time of consultation for study, after consent and after treatment with a minimum follow-up of 3 months after randomisation
Main (if funded)	Primary	As above	At time of progression or failure judged clinically or maximum 5 years follow-up after randomisation
Main (if funded)	Secondary	As above	Up to and including 5 years from randomisation

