5.9 Follow-up

Follow-up will consist of serum Prostate Specific Antigen (PSA) tests at 3 months and 12 months after completion of treatment as defined above. Thereafter, PSA will be measured 6-monthly until a progression event is determined, for 5 years after initial randomisation or mortality (whichever is first).

Patient reported outcome measures (PROMs) will be collected at 3 and 12 months and then annually thereafter until progression, mortality or 5 years after initial randomisation (whichever is first). The minimum follow-up for each patient will be 5 years in the main study although yearly follow-up will continue long term in clinical standard care through linkage to national databases.

NB: if the trial does not proceed to the Main Stage following the analysis of the Pilot, patients will be followed up for a minimum of 3 months and will then revert to standard of care in which the clinical care provided to patients will not differ from the clinical follow-up stipulated in this protocol. At the end of the study patients will continue to be followed up locally within their recruitment centres within the ICE (European Registry for Cryosurgical Ablation of the prostate, EuCAP) or the HEAT international HIFU registry as per NICE guidelines IPG432/IPG42.

Patient reported outcome measures

The EORTC QLQ-C30 with the prostate-specific module, International Prostatic Symptoms Score (IPSS), EPIC bowel and bladder and International Index of Erectile Function 15 (IIEF15) will be used.

The EuroQol (EQ-5D) will be used in the study as a generic measure of health-related quality-of-life which can be linked to public preferences. These data will be used to calculate quality-adjusted life-years as part of a future health economic evaluation. Patients agreeing to return questionnaires on quality of life should continue to complete quality of life data for 5 years after randomisation. Questionnaires should be self-administered, although it is recommended that a key person (e.g. research nurse) at each centre be responsible for the data collection to optimise compliance and completeness of the data.

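### CHRONOS-B's 120 control events within 7.6 years assume follow-up past 5 years, but the follow-up rules conflict and the 5-year minimum does not fit the timeline

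*Protocol*

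**What the plan says.** **The projection.** Protocol section 8.1.2 sizes CHRONOS-B as follows: "we anticipate approximately 1200 patients are required over 5 years". The aim of that number is "to observe 120 control arm failure-free survival (FFS) events within 7.6 years". Men are randomised "with an allocation ratio of 1:1:1". The projected time "is based on an assumption of 20 patients recruited per month", with 20% of men failing by 3 years and 30% by 5 years, and is said to depend on the event rates observed. The 85% power for a hazard ratio of 0.67 is attached to the efficacy-stage analysis. Section 8.3 triggers that analysis by the number of control-arm events (Table 2: about 120).

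**Follow-up.**
- Section 2.7, primary endpoint, main stage: "At time of progression or failure judged clinically or maximum 5 years follow-up after randomisation".
- Section 5.9, PSA testing: until progression, or "for 5 years after initial randomisation or mortality (whichever is first").
- Section 5.7, visit schedule: the last visit is 60 months after visit 2, which is dated from the end of treatment.
- Section 5.9, a little further on: "The minimum follow-up for each patient will be 5 years in the main study", with yearly follow-up continuing in standard care through national databases.
- Section 8.3: men without an event are censored when last seen or known alive. No 5-year limit is given.

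**Calendar.** The Trial Summary (Duration) allows 12 months of pilot recruitment and then: "Main study: Recruitment further 48 months. Total including follow-up = 96 months". Section 8.2 has recruitment finished within 5 years and the primary analysis after 8.

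**The concern.** One follow-up duration appears as a maximum in section 2.7 and as a minimum in section 5.9. The event projection fits neither. To reach 120 control events at 7.6 years, early recruits must contribute events after year 5, which the maximum excludes. A minimum of 5 years for every man cannot be met when recruitment takes 5 of the 8 years.

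The date of the final CHRONOS-B analysis is at stake, and possibly whether its trigger can be reached. If sites stop collecting FFS at 5 years, as section 2.7 allows, events come more slowly than section 8.1.2 projects, and nothing is in reserve for men lost to follow-up.

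**Working it through.** **Inputs** (section 8.1.2): 20 men per month at 1:1:1, so 80 control men per year for 5 years, 400 in total. The hazard is λ = −ln(0.70)/5 = 0.0713 per year (30% by 5 years) or λ = −ln(0.80)/3 = 0.0744 (20% by 3 years). No loss to follow-up is stated for CHRONOS-B, so none is assumed until step 4.

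**1. Reproducing the plan's figure: no limit on follow-up.** Expected control events at time T are 400 × {1 − [e^(−λ(T−5)) − e^(−λT)]/(5λ)}.
- 30% by 5 years, T = 7.6: 400 × {1 − (0.8307 − 0.5815)/0.3567} = **120.5**.
- 20% by 3 years: **124.7**.
- Curves through both points: 120.5 (piecewise exponential) and 120.3 (Weibull).

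The stated 120 at 7.6 years is therefore an uncapped figure. Men recruited before year 7.6 − 5 = 2.6, which is 2.6/5 = 52% of them, are counted beyond 5 years.

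**2. Follow-up stopped at c years.** Expected events are 80 × {(T−c)(1 − e^(−λc)) + (5 − T + c) − [e^(−λ(T−5)) − e^(−λc)]/λ}. For c = 5, T = 7.6 and 30% by 5 years: 80 × {2.6 × 0.30 + 2.4 − (0.8307 − 0.7000)/0.0713} = 107.8.

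| Stop at 5 years from randomisation | 30% by 5 y | 20% by 3 y |
|---|---|---|
| Events at 7.6 y | 107.8 | 111.7 |
| Events at 8.0 y | 111.6 | 115.6 |
| Events at 10 y (maximum) | 120.0 | 124.2 |
| Time of 120th event | 10.0 y | 8.6 y |

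If the 60 months run from visit 2, assumed to fall 0.25 to 0.5 years after randomisation (c = 5.25 to 5.5), events at 7.6 years are 110 to 116. Setting the same formula to 120 gives 7.9 to 8.7 years.

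**3. Power.** The control-event formula is Φ{[|ln 0.67| − 1.96√(2/e₀)]/√(1/e₀ + 1/e₁)}, where e₀ is control events and e₁ is research-arm events at hazard 0.67λ.
- At e₀ = 120, e₁ = 85: (0.4005 − 0.2530)/0.1418 = 1.04, giving **85.1%**, the stated power. At 47 control events the same formula returns the stated interim critical hazard ratio (0.974) and interim power (95%). A Schoenfeld calculation on total events gives 82% at 120 + 85, so it is not the plan's method.
- Analysis held at 7.6 years with the 5-year stop: e₀ = 107.8, e₁ = 76.0 gives 81.4%; e₀ = 111.7, e₁ = 78.9 gives 82.6%. With the stop dated from visit 2: 82 to 84%.

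**4. Loss to follow-up.** Borrowing the 5% that section 8.1.2 uses for CHRONOS-A (an assumption here), 380 control men give a capped maximum of 380 × 0.30 = 114 or, at the other rate, 380 × 0.3106 = 118. Both are below 120.

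**5. The 5-year minimum.** Recruitment of 12 + 48 = 60 months plus 60 months of follow-up needs 120 months. Within 96 months the last man has 96 − 60 = 36 months, or 48 if the 96 months exclude the pilot. At 7.6 years he has 2.6 years, about 31 months.

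**The case against.** A reader might infer that the 85% power is simply not delivered. The documents do not support that. Section 8.1.2 ties the power to the efficacy-stage analysis and makes 7.6 years depend on observed event rates, and section 8.3 triggers the analysis by events. At 120 control events the power is 85% with or without a cap. The 81 to 83% belongs to an analysis forced at 7.6 years, which the protocol does not plan.

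A reader might also take the 5-year cap as settled. It is not. Only the section 2.7 table applies it to the primary endpoint. The section 5.9 stop governs PSA testing, and the CHRONOS-B failure definition has no PSA component. Visits end 60 months after treatment, somewhat later than 5 years from randomisation. The minimum in section 5.9, its continuing linkage and the censoring rule in section 8.3 all point the other way. This stands: it is a contradiction to reconcile. Linkage does not resolve it, because consent to it is optional (sections 5.10 and 6.11) and no section says it will supply FFS events such as repeat focal therapy.

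Sections 8.1.1 and the Trial Summary give 1260 patients for CHRONOS-B. With 420 per arm, capped events at 7.6 years are 113 to 117 and power is 83 to 84%, so the shortfall is smaller but remains. The main stage also depends on funding, and section 8.2 allows its timelines to be revised after the pilot. That makes the correction easy; it does not make the present statements agree.

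**Conclusion.** The point holds as an inconsistency with a modest, quantifiable effect. The stated event count, its date and the follow-up rules cannot all be true.

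- The 5-year minimum cannot be met on either reading of the 96 months.
- If the 5-year maximum from randomisation applies with 400 per arm, the projection at 7.6 years is 7 to 10% too high. The 120th control event moves by 1 to 2.4 years, past the stated 96 months. If the limit runs from visit 2, the delay is smaller and the 96 months may or may not suffice.
- At 30% failing by 5 years the capped maximum is exactly the number required, so any loss puts the trigger out of reach. At 20% by 3 years there is a margin of about 4 events, which a 5% loss would remove.
- Power falls by 2.4 to 3.6 points only if the analysis is done at 7.6 years without waiting for 120 events.

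These figures assume uniform accrual, a constant hazard at each stated rate, and no loss except where the 5% is applied.

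**What to change.** State one follow-up rule for FFS and PFS, in the same terms in sections 2.7, 5.7 and 5.9, and say in section 8.1.2 which rule the 7.6-year projection assumes. Either:

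(a) delete the 5-year maximum and follow all men for FFS until the 120-event trigger, through trial visits or standard-care follow-up reported to the trial, without relying only on optional-consent linkage; or

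(b) keep the 5-year maximum and restate the expected events together with either the analysis date (about 8.6 to 10 years) or the power at the planned date, with a stated allowance for loss.

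Under either option, replace the 5-year minimum with what the timeline permits for the last man (about 2.6 years at 7.6 years, 3 years at 96 months), or lengthen the 96 months. If the minimum is shortened, say how the Trial Summary's aim of FFS and PFS at 5 years will be met, since at 7.6 years only about 52% of men could have reached 5 years.

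The cost is protocol wording plus, under (a), longer follow-up of early recruits or, under (b), a later date or slightly lower stated power. No extra patients are needed.
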